#### 6.3.2 Sensitivity analysis

All secondary outcomes will be subject to adjusted mixed effects regression analysis with time not included within the models as a random effect to assess the robustness of the conclusions to the timing of follow-up. The key secondary outcomes, MHQ and range of motion of the treated digit, will have a sensitivity analysis carried out on a PP basis to determine the effect of changes in procedures under which the intervention was received. CACE analysis will also be used to assess data quality and the impact of compliance on these key secondary outcome measures.

For those who have progressed to surgery, an analysis excluding participants where it is not known which digit was operated on will be undertaken.

For sensitivity analyses related to Covid-19, see **Appendix 6: Response to SARS-CoV-2 Pandemic (Covid-19)**.

### 6.4 Analysis methods: Tertiary and exploratory outcomes

For the analysis of circulating levels of adalimumab and antibodies to adalimumab in the blood (tertiary objective), we will report circulating levels of adalimumab by treatment arm. The mean difference between levels recorded at baseline, 3-months and 12-months in those who received at least one adalimumab injection will be explored.

Repurposing anti-TNF for treating Dupuytren's disease (funded by Health Innovation Challenge Fund, Wellcome Trust)

EudraCT Number: 2015-001780-40 and OCTRU Reference Number CTU0028

For the analysis of changes in other molecular markers and biomarkers in the blood (exploratory objective), the mean difference between levels recorded in the two treatment groups at baseline, 3-months and 12-months will be reported.

If the data are normally distributed a t-test to assess for significant differences between levels at 3-months and 12-months will be applied. If the data are not normally distributed, the data will be log-transformed in order to gain normality and geometric means with 95% confidence intervals will be reported. If data is not normally distributed after log-transformation, the non-parametric Mann-Whitney test will be used with no adjustment for baseline, and the median change with 95% confidence intervals will be reported. Where significant differences are identified, correlations between the tertiary and exploratory outcomes and the primary outcome will be carried out. Further explorations of tertiary outcomes may include: (1) additional adjustments to the primary outcome model by including circulating levels as continuous covariates, and (2) further regression modelling to directly explore associations between grouped levels – using ordered categorisation – and the primary outcome.

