## **Part 2. Randomised controlled trial**

For the randomised controlled part of the trial, participants will be recruited with **early DD** to assess the efficacy of injections of adalimumab in controlling disease progression including nodule hardness.

A maximum of 200 participants will be randomised to participate in the study if they meet the inclusion/exclusion criteria and provide written consent. We will select participants with early disease nodules who also give a clear history of activation and progression of the disease in the previous 3-6 months. Only participants with flexion deformities of  $\leq 30^\circ$  at the metacarpophalangeal and/or at the proximal interphalangeal joint of their fingers will be recruited, with a maximum total flexion deformity of  $60^\circ$ . All participants will be screened for TB, Hepatitis B and C and HIV. If results are positive for any test, the participant will not be eligible to enter the trial and will be informed and counseled about the result of their test. The participants will be randomised (1:1) to receive injections of either adalimumab or saline (placebo) into the active nodule. The dose will be an injection into the nodule of 40 mg adalimumab, or the equivalent volume of saline. The adalimumab formulation of 40 mg in 0.4 ml formulation will be used. The adalimumab or placebo will be administered at 3 monthly intervals for the first year i.e. each participant will be injected on 4 occasions over a 9 month period (baseline, 3, 6 and 9 months) and followed-up for a further 9 months. If, on a returning visit, the nodule has reduced in size to such an extent that the clinician is not satisfied they can accurately deliver a repeat injection, then the clinician may decide to not inject on that visit. In this event, the participant will be invited to all further visits as originally planned, and future planned injections may be given if the nodule recurs.

Study participants will be seen at 6 time points after screening: week 0, 3 months, 6 months, 9 months, 12 months and 18 months according to the flow chart (Appendix B: Trial Flow Chart Part 2). The schedule, duration of each visit and visit window is detailed in the Schedule of procedures (Appendix C: Schedule of procedures Part 2). Study participants will be contacted by telephone by a member of the research team at 1 week post baseline to monitor for Adverse Events.

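### SAP 6.4 pools 12-month adalimumab levels regardless of whether the 9-month injection was given, so drug persistence is mixed with doses omitted because the nodule shrank

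*SAP*

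**What the plan says.** SAP 6.4 reports levels by arm and then looks at change across visits in anyone who had adalimumab: "levels recorded at baseline, 3-months and 12-months in those who received at least one adalimumab injection will be explored". A t-test, with log-transformed and rank-based fallbacks, is applied to the 3- and 12-month levels. Next: "Where significant differences are identified, correlations between the tertiary and exploratory outcomes and the primary outcome will be carried out". Optional further models include "additional adjustments to the primary outcome model by including circulating levels as continuous covariates". No step mentions the number of injections, receipt of the 9-month injection or time since the last dose. The population for the correlation is not stated.

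Protocol section 6 (Part 2) schedules injections at baseline, 3, 6 and 9 months. The exception applies where "the nodule has reduced in size to such an extent that the clinician is not satisfied they can accurately deliver a repeat injection"; whether to omit the dose is left to clinical judgement. The omission can be reversed: "future planned injections may be given if the nodule recurs". Protocol 8.6 repeats the exception at the 3-month visit and carries it over to the 6- and 9-month visits.

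Research blood is taken at baseline, 3 and 12 months (Protocol 8.7). Each injection date goes on the CRF (Protocol 9.4). SAP 6.1 hopes the levels will inform how often to inject, and notes that anti-drug antibodies may go with lower efficacy. SAP Appendix 5 tabulates injections received, and 12-month hardness by number of injections. It has no table of drug level by dosing history.

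**The concern.** At the 3-month sample everyone treated is about three months from exactly one injection. No dose can have been omitted by then, and Protocol 8.6 lists that blood before the visit's injection. At 12 months the group is mixed. Those injected at 9 months are about three months from their last dose; those not injected are six months or more from it. Where the reason was shrinkage, the low level is partly a consequence of nodule response.

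Two readings are then at risk. A fall between 3 and 12 months could be taken as loss of exposure, for example through antibodies, when part of it is undelivered doses. A level-hardness association could be taken as exposure-response when part of it runs from nodule to dosing to level. Both bear on the use SAP 6.1 has in mind, the choice of injection interval. Restricting to the adalimumab arm does not remove the problem, because it arises within that arm.

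**Working it through.** **Plan's own figure.** The documents give no figure for the level analysis. The Part 2 sample size supplies the number of participants. With effect size 0.62, 5% two-sided and 90% power, n = 2 × (1.960 + 1.282)² / 0.62² = 54.7, so 55 per arm. Then 55/0.8 = 68.75, so 69 per arm and 138 in total, as stated. About 55 adalimumab completers are therefore expected at the minimum size, and 100 × 0.8 = 80 at the maximum of 200 participants.

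**Step 1: how far a missed injection lowers the 12-month level.** Inputs from the documents: doses 364, 273, 182 and 91 days before the 12-month sample. The half-life is not given; 10, 14 and 20 days are assumed. Level = sum over given doses of 2^(−days/half-life). With r = 2^(−91/half-life), the fully dosed level is r + r² + r³ + r⁴. Without the 9-month dose it is r² + r³ + r⁴, so the ratio is close to r.

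| Half-life (days) | Fully dosed level, as share of level just after one dose | Ratio, 9-month dose omitted | Ratio, only 6-month dose omitted |
|---|---|---|---|
| 10 | 0.2% | 0.2% | 99.8% |
| 14 | 1.1% | 1.1% | 98.9% |
| 20 | 4.5% | 4.3% | 95.9% |

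Omitting only the 3-month dose leaves over 99.8%. Only the 9-month injection matters materially.

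**Step 2: pooled mean.** If a share w missed the 9-month injection, the shortfall is w × (1 − ratio). For w = 10% and half-life 14 days this is 0.10 × 0.989 = 9.9%. For w = 20% and half-life 20 days it is 0.20 × 0.957 = 19.1%. This needs no link between size and hardness, and applies whatever the reason for omission. The documents give no value for w.

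**Step 3: correlation with hardness when level has no effect.** Simulation of 200,000 participants per setting. Assumptions: half-life 14 days, between-person CV 50%, sampling-time SD 10 days, the smallest nodules not injected. Spearman correlation of 12-month level with hardness:

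| Share without 9-month injection | Size-hardness correlation 0 | 0.3 | 0.6 |
|---|---|---|---|
| 2% | 0.00 | +0.02 | +0.04 |
| 5% | 0.00 | +0.05 | +0.10 |
| 10% | 0.00 | +0.09 | +0.18 |
| 20% | 0.00 | +0.15 | +0.29 |
| 30% | 0.00 | +0.19 | +0.38 |

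At 10% and 0.3, half-lives of 10, 14 and 20 days all give about +0.09. An assay floor at the typical fully dosed level reduces this to about +0.05.

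The chance of a significant positive result is roughly Φ(atanh(r) × √(n − 3) − 1.96), against 2.5% in that direction under no association. For n = 55 it is roughly 10% to 25% at r = 0.09 to 0.18, and 61% at r = 0.30. For n = 80 it is 78% at r = 0.30.

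A simpler model used one nodule-state variable, with levels lowered by 1 to 3 SD when a dose is withheld and n = 55. False positives ran from 6% (10% withheld, correlation 0.3, 1 SD) through 36% (20%, 0.5, 2 SD) to 82% (20%, 0.7, 3 SD), against a nominal 5%.

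**Step 4: the remedy.** Restricted to those given the 9-month injection, the spurious correlation in the first model lies between −0.004 and +0.004 in every setting.

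**The case against.** A reader might infer that responders have lower levels by design and that the correlation is therefore biased towards more drug, harder nodule. The documents do not support that.

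- **Not all responders.** Omission is discretionary and reversible, and applies only when shrinkage prevents accurate injection. Only a missed 9-month dose matters. No expected frequency is given.
- **Size, not hardness.** The trigger is size and the outcome is hardness. The documents do not quantify the link; without one the correlation bias is zero.
- **Direction not fixed.** Antibodies that lower both level and efficacy (SAP 6.1) push the other way. If both arms enter the correlation, near-zero placebo levels combined with any benefit do too. The simulations contain only one pathway, so their positive sign is built in.
- **Chosen inputs.** The 36% figure needs 20% withheld, a correlation of 0.5 and a 2 SD drop. The low end, 6%, is close to nominal.

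These points stand and limit the claim. Three others carry less weight. SAP 4.1 makes such outcomes exploratory and hypothesis generating, which lowers the stakes but does not correct the pooled summary. SAP section 1 leaves further exploratory splits open, yet none is planned for drug level. The correlation runs only after a significant difference, but omitted 9-month doses can themselves create a 3- versus 12-month difference, so that condition gives no protection.

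**Conclusion.** The point holds in limited form. SAP 6.4 ignores dosing history, while Protocol section 6 lets dosing depend on nodule size. The pooled 12-month mean is lower by roughly the share who missed the 9-month injection: about 10% to 19% in the cases worked, where 10% or 20% miss it. If smaller nodules are also softer, this mechanism pushes the level-hardness correlation towards higher level with harder nodule, by +0.02 to +0.38 over the settings tried. Omission rate, half-life, size-hardness link and level variability are all assumptions, so neither the size nor the net direction of the bias can be established from the documents. The analysis is tertiary. The primary intention-to-treat result is unaffected unless level is added through the optional covariate model. This is a cheap improvement worth making, not a threat to the trial's main conclusion.

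**What to change.** Amend SAP 6.4:

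- Make the 3- versus 12-month level comparison in adalimumab participants who received the 9-month injection. Show the others separately, with the number of injections and the reason for omission.
- Give days since last injection for everyone. At an assumed 14-day half-life, a 28-day shift, which the visit windows in Protocol Appendix C allow, changes the level by a factor of 2^(28/14) = 4.
- State that the level-outcome correlation is within adalimumab recipients. Base it on the 3-month level, which precedes any omitted dose, adjusted for baseline hardness.
- Report any association with the 12-month level only among those given the 9-month injection, labelled descriptive and non-causal. Receipt of that injection is enough; requiring all four would discard data needlessly. Label the optional covariate and grouped-level models the same way.

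The cost is SAP wording; the injection dates are already on the CRF. The downside is a smaller 12-month sample: of 55 completers, 44 to about 50 if 10% to 20% had no 9-month injection. It is also selected towards nodules that remained injectable, which the report should say.

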Monitor for adverse events	Adverse event monitoring comparing active and placebo groups using visual inspection of injection site.	Observation at week 0 and 3, 6, 9 and 12 months.
Tertiary Objectives To assess if early DD injection therapy represents good value for money compared to current clinical care.	Analysis of EQ-5D-5L data to estimate utilities using quality-adjusted life years (QALYs) from participants on each treatment. Analysis of resource use data to estimate the cost of each treatment.	EuroQol EQ-5D-5L before, and at 3, 6, 9, 12 and 18 months after first treatment.
To determine circulating levels of adalimumab and antibodies to adalimumab in the blood.	Monitor circulating levels of adalimumab and antibodies to adalimumab in the blood.	Analysis of blood samples pre-injection and 3 and 12 months post first treatment.
Exploratory Objective To investigate changes in other molecular markers relevant to the progression of Dupuytren's disease.	Change in level of the markers.	Analysis of blood samples taken pre-injection and at 3

		and 12 months post first treatment.
--	--	-------------------------------------

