**Part 1 and Part 2**

**Blood:** The participants in the trial will have:

**Part 1:** A maximum of 12.5ml of blood collected at baseline and 2 weeks post-injection will be sent to the NDORMS laboratories in Oxford.

**Part 2:** A maximum of 12.5ml of blood collected at baseline, 3 months, and 12 months post first injection, will be sent to the NDORMS laboratories, in Oxford.

The transportation procedure is described in the Sample Handling Manual. On arrival the serum will be stored at -80 degrees Celsius. Serum concentration of adalimumab and antibodies to adalimumab will be measured using a commercial ELISA kit.

Participants will have provided informed consent approving collection, long-term storage, and future use of tissue and blood. As new mechanisms of action, safety and efficacy may evolve during or following the trial, which are unknown at present, biospecimens will be stored for a maximum of 15 years from the end of trial, after which time they will be destroyed. All samples will be identified by a trial identification number and stored securely.

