To monitor circulating levels of adalimumab and antibodies to adalimumab in the blood						
Monitor circulating levels of adalimumab and antibodies to adalimumab in the blood	*	*				*
Exploratory objective						
To investigate changes in other molecular markers relevant to the progression of DD e						
Change in level of the markers	*	*				*

a ± 2 weeks | b ± 4 weeks | c where participants' 12- or 18-month data collection was delayed due to SARS-CoV-2 pandemic, the outcomes recorded via questionnaires should be completed within ± 4 weeks and the physical measurements should be completed within ± 3 months, where it is safe to do so, with additional questionnaires completed at the point of delayed physical outcomes measurement | d the nodule hardness secondary objective will account for all timepoints where this information has been collected, including the primary end-point of 12 months | e analysed by health economist

Repurposing anti-TNF for treating Dupuytren's disease (funded by Health Innovation Challenge Fund, Wellcome Trust)  
EudraCT Number: 2015-001780-40 and OCTRU Reference Number CTU0028

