## 5.3 Baseline Comparability of Randomised Groups

The patients in the two treatment arms will be described both overall and separately in terms of stratification factors (centre and age).

Numbers (with percentages) for binary and categorical variables and means (and standard deviations), or medians (with lower and upper quartiles) for continuous variables will be presented; there will be no tests of statistical significance nor confidence intervals for differences between randomised groups on any baseline variable.

**Appendix 5: Baseline comparability of randomised groups, Table 3:** Categorical demographic baseline characteristics according to intervention allocated.

**Appendix 5: Baseline comparability of randomised groups, Table 4:** Continuous demographic baseline characteristics according to intervention allocated.

**Appendix 5: Baseline Comparability of randomised groups, Table 5:** Clinical characteristics according to intervention allocated.

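### The exploratory marker outcome is change, but the analysis in SAP 6.4 is written on levels, leaves the pre-injection value out of the treatment comparison, and is unclear about which contrast is tested

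*SAP*

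**What the plan says.** SAP 3.5, Table 1 gives the exploratory outcome as "Change in level of the markers", and the Part 2 objectives table in Protocol section 5 names it the same way. The timing entry in that protocol table begins "Analysis of blood samples taken pre-injection and at 3" and goes on to the 12-month sample. Protocol 8.7 schedules the blood for this: "A maximum of 12.5ml of blood collected at baseline, 3 months, and 12 months post first injection".

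SAP 6.4 introduces the exploratory analysis as one of changes in markers, and then sets out these steps:

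- Summary: "the mean difference between levels recorded in the two treatment groups at baseline, 3-months and 12-months will be reported".
- Test, if the data are normally distributed: "a t-test to assess for significant differences between levels at 3-months and 12-months will be applied".
- If not, a log transformation. If that also fails: "the non-parametric Mann-Whitney test will be used with no adjustment for baseline, and the median change with 95% confidence intervals will be reported".
- Follow-on step: "Where significant differences are identified, correlations between the tertiary and exploratory outcomes and the primary outcome will be carried out".

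No change score, baseline covariate or repeated-measures model is stated for the markers. By contrast, the primary analysis in SAP 6.2 is ANCOVA with baseline nodule hardness, and the secondary models in SAP 6.3 carry the baseline measurement as a fixed effect even in the analysis labelled unadjusted.

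**The concern.** The outcome is defined on change, while the main analysis route is written on levels. Three things follow.

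1. The pre-injection sample is collected but is not used in the treatment comparison. A chance difference between arms at baseline therefore carries through, in proportion to the baseline-to-follow-up correlation, into the contrasts at 3 and 12 months. Stable variation between people also stays in the error term.
2. The t-test wording does not fix the contrast. It can mean adalimumab against saline at each visit, or the 3-month visit against the 12-month visit. The second is not a treatment comparison.
3. The Mann-Whitney fallback rules out baseline adjustment and yet reports a median change. A test on levels paired with an estimate on change would describe two different quantities.

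The downstream stake is the gating. A marker is correlated with the primary outcome only after a significant result, so avoidable imprecision influences which markers are followed up.

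**Working it through.** **Inputs.** The documents give no SD, power or sample size for any marker, and no correlation between the pre-injection and follow-up levels. That correlation, r, is an assumption, shown from 0.2 to 0.8. Equal SDs at baseline and follow-up are also assumed. Allocation is 1:1 (SAP 3.2).

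**The plan's own figure.** The stated size belongs to nodule hardness (SAP 3.3) and serves here only to give a realistic number per arm. With effect size 0.62, two-sided 5% and 90% power:

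n per arm = 2 × (1.960 + 1.282)² / 0.62² = 54.7, so 55. Allowing for 20% loss, 55 / 0.8 = 68.75, so 69 per arm and 138 in total. The stated 138 reproduces. The illustrations below use 55 evaluable participants per arm.

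**Relative variance of the between-arm estimate** (raw follow-up level = 1):

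- change score: 2(1 − r)
- ANCOVA on the baseline level: 1 − r²
- narrowing of the confidence interval, ANCOVA against raw level: 1 − √(1 − r²)

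| assumed r | raw level | change score | ANCOVA | ANCOVA interval narrower by |
|---|---|---|---|---|
| 0.2 | 1 | 1.60 | 0.96 | 2% |
| 0.3 | 1 | 1.40 | 0.91 | 5% |
| 0.5 | 1 | 1.00 | 0.75 | 13% |
| 0.7 | 1 | 0.60 | 0.51 | 29% |
| 0.8 | 1 | 0.40 | 0.36 | 40% |

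**Detectable difference** with 90% power and 55 per arm is (1.960 + 1.282) × √(2v/55), where v is the relative variance. For raw levels it is 0.618 SD. For ANCOVA it is 0.606, 0.535 and 0.371 SD at r = 0.2, 0.5 and 0.8. For a change score it is 0.782, 0.618 and 0.391 SD.

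**Chance imbalance.** The baseline mean difference has standard error √(2/55) = 0.19 SD. At r = 0.7, an imbalance of that size moves the raw follow-up contrast by 0.7 × 0.19 = 0.13 SD. At r = 0.3 it moves it by 0.3 × 0.19 = 0.06 SD.

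**Expectation.** A simulation of 20,000 trials (55 per arm, true difference −0.5 SD) gave a mean estimate of −0.499 for raw level, change score and ANCOVA alike, at both r = 0.3 and r = 0.7. The empirical standard errors, in that order, were 0.190, 0.226 and 0.182 at r = 0.3, and 0.191, 0.146 and 0.135 at r = 0.7. The three methods estimate the same between-arm effect and differ in precision.

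**Level or change in ANCOVA.** Regressing change on arm and baseline, Y − B = a + bT + cB, rearranges to Y = a + bT + (c + 1)B. The arm coefficient b is the same either way, so ANCOVA on the follow-up level also answers a question posed as change.

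**The case against.** The strongest reply is that nothing is biased. Arms are randomised, so with complete data the difference in mean follow-up level has the same expected value as the difference in mean change, and its standard error already allows for chance imbalance. This stands. A reader might infer that the analysis as written fails to estimate the planned quantity; for the between-arm effect that is not so. What the main route lacks is change within participants and a contrast corrected for the imbalance actually observed.

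A second reply is that the text may not mean a raw comparison of arms at all. The preceding tertiary sentence in SAP 6.4 uses nearly the same phrase for adalimumab recipients only, where it can only mean differences between visits. The exploratory sentence might be meant likewise. This also stands. The comparison of arms on levels is a plausible reading, not an established one, and the ambiguity is part of the point.

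Three further inferences go beyond the documents:

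- That the pre-injection sample is ignored. Baseline levels are reported, and the last fallback reports a change.
- That SAP 5.3 is contradicted. It says that "there will be no tests of statistical significance nor confidence intervals for differences between randomised groups on any baseline variable". SAP 6.4 reports a baseline difference but names only 3 and 12 months for the test.
- That moving to change scores would by itself improve precision. It does so only for r above 0.5; below that, a change score is less precise than the raw level.

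Finally, SAP 4.1 treats these outcomes as exploratory, and Protocol section 4 gives other endpoints priority when blood is limited, so marker data may be incomplete. Both limit the consequence. Neither is a reason to leave the baseline value out.

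**Conclusion.** The concern holds as a matter of specification and efficiency, not bias. SAP 6.4 does not match the named outcome clearly, does not fix the t-test contrast, pairs an unadjusted test with a median change, and omits the baseline covariate that the primary and secondary analyses use.

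The gain from ANCOVA over raw levels runs from about 2% narrower intervals at r = 0.2 to about 40% at r = 0.8. It rests wholly on the assumed r and on equal SDs; at r = 0 there is no gain, and one degree of freedom is spent. The direction does not depend on r beyond that.

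Priority is low. No confirmatory conclusion depends on the markers. The one planned consequence is which markers go forward to the correlations with nodule hardness.

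**What to change.** In SAP 6.4, for the exploratory markers:

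- State that, for each marker, the difference between arms at 3 and at 12 months will be estimated by ANCOVA of the follow-up level on treatment arm and the participant's pre-injection level, with a 95% confidence interval. A mixed model with the same baseline covariate would also serve. Log-transform both levels where needed and report a ratio of geometric means.
- Let this replace the t-test, which also settles that arms, not visits, are compared.
- Show baseline levels by arm descriptively only.
- Apply the Mann-Whitney fallback to change from baseline, so that the test and the reported median change refer to the same quantity.
- Add a simple rule for participants without a usable pre-injection marker value.

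The cost is a few sentences of SAP wording, settled before unblinded analysis. No new samples or visits are needed, and the method is the one already planned for the primary outcome.

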### 3.3 Sample Size

The sample size is based on unpublished data acquired in a pilot study 'Ultrasonographic (grey scale) characteristics of DD and their relationship to the clinical features and functional severity of the disease: a pilot study' (REC Ref. 11/SC/0447). Within the study there were 25 participants with mean nodule hardness of  $53 \pm 8$  for participants suffering DD and  $32 \pm 3$  for corresponding controls matched by age and sex.

Using the study, a minimum of 138 participants (69 per arm) would be required to detect a moderate effect size of 0.62, based on a 5 point change in nodule hardness at 12 months and assuming a standard deviation of 8 (5% significance (2-sided) and 90% power, allowing for a 20% loss to follow up).

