## 4. STATISTICAL PRINCIPLES

### 4.1 Statistical Significance and Multiple Testing

There is no multiple testing as only a single primary objective is considered. Therefore, significance levels used will be 5%, and 95% confidence intervals will be reported. Secondary outcomes will also be analysed using a significance level of 5% and 95% confidence intervals as these are considered supportive of the primary conclusion only. Other outcomes will be considered exploratory and hypothesis generating only.

No interim analysis of primary and secondary endpoints are planned but, if requested by the DSMC, a 0.1% significance ( $\alpha=0.001$ ) will be used.

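### SAP 6.4 gives one test paragraph to a paired comparison and an unpaired one; its Mann-Whitney fallback does not suit adalimumab levels at 3 versus 12 months in the same participants

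*SAP*

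**What the plan says.** SAP 6.4 first deals with circulating adalimumab, a tertiary outcome. Levels are to be reported by arm, and then: "The mean difference between levels recorded at baseline, 3-months and 12-months in those who received at least one adalimumab injection will be explored". For the exploratory markers the stated contrast is different: "the mean difference between levels recorded in the two treatment groups at baseline, 3-months and 12-months will be reported".

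A single paragraph on testing follows. It opens with "If the data are normally distributed a t-test to assess for significant differences between levels at 3-months and 12-months will be applied". Non-normal data are to be log-transformed, and if that fails "the non-parametric Mann-Whitney test will be used with no adjustment for baseline, and the median change with 95% confidence intervals will be reported". The paragraph then makes correlations with the primary outcome conditional on a significant difference, and there it refers to the tertiary and the exploratory outcomes together. It ends with further optional explorations: circulating levels as covariates in the primary model, and regression of the primary outcome on grouped levels. Neither is conditional on significance.

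Protocol 8.7 (Sample Handling) and the Part 2 schedule in Protocol Appendix C show that each Part 2 participant gives research blood at baseline, 3 months and 12 months.

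**The concern.** Once the drug-level comparison is restricted to adalimumab recipients, there is no second independent group. Visit is the only grouping left, and the same people contribute to both visits. Mann-Whitney takes its null variance from two independent samples and ignores the covariance between a person's two values. Section 6.4 names no paired t-test, signed-rank test or repeated-measures model, so an analyst who follows the paragraph literally for drug levels reaches an independent-samples test on paired data.

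At stake is power. If levels are positively correlated within a person, a real change between 3 and 12 months is more easily missed, and the correlations that depend on significance would then not be run.

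**Working it through.** **Inputs**

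- Contrast for drug levels: across visits, adalimumab recipients only (SAP 6.4).
- Contrast for markers: between arms (SAP 6.4).
- Named tests: a t-test of unspecified type, then Mann-Whitney (SAP 6.4).
- Significance level: SAP 4.1 sets none for tertiary outcomes, saying "Other outcomes will be considered exploratory and hypothesis generating only". Two-sided 0.05 is assumed.
- Number of pairs: taken from SAP 3.3, "a minimum of 138 participants (69 per arm) would be required to detect a moderate effect size of 0.62", with 20% loss.
- Within-person correlation ρ between 3 and 12 months: not given. It is assumed, with 0 to 0.9 examined.

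**Step 1: number of pairs.** Section 6.4 states no figure to reproduce, so the only plan figure checked is the sample size. A two-sample t calculation for a difference of 5, SD 8, 90% power and two-sided 5% gives 54.8, so 55 per arm. Then 55 / 0.8 = 68.75, so 69 per arm and 138 in total, which matches the plan. The illustration therefore uses n = 55 pairs.

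**Step 2: analytic check for an unpaired comparison of means.** With equal variance σ² at both visits, the difference in means has true variance 2σ²(1 − ρ)/n, while an unpaired test assumes 2σ²/n. Hence:

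- SE ratio (assumed / true) = 1/√(1 − ρ)
- actual two-sided α = 2[1 − Φ(1.96/√(1 − ρ))]

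| ρ | SE ratio | Actual α |
|---|---|---|
| −0.3 | 0.88 | 0.086 |
| 0 | 1.00 | 0.050 |
| 0.3 | 1.20 | 0.019 |
| 0.5 | 1.41 | 0.006 |
| 0.7 | 1.83 | 0.0004 |

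These figures belong to an unpaired t-test. The rank test was simulated separately.

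**Step 3: simulation of the named fallback.** 10,000 runs, 55 pairs, bivariate normal with equal SDs, Mann-Whitney against Wilcoxon signed-rank.

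| ρ | Type I error, Mann-Whitney | Type I error, signed-rank | Power at 0.4 SD, Mann-Whitney | Power at 0.4 SD, signed-rank |
|---|---|---|---|---|
| 0 | 0.048 | 0.049 | 0.53 | 0.52 |
| 0.3 | 0.023 | 0.053 | 0.54 | 0.68 |
| 0.5 | 0.007 | 0.052 | 0.54 | 0.81 |
| 0.7 | 0.0006 | 0.050 | 0.55 | 0.96 |

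At ρ = 0.9, Mann-Whitney's type I error is about 0 and signed-rank's is 0.048. Signed-rank holds its level throughout. Mann-Whitney becomes steadily more conservative as ρ rises and does not gain the power that pairing offers.

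The simulated data are normal, whereas the plan reaches this fallback only after normality has failed, so the figures illustrate direction and rough size.

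**The case against.** The strongest reply is that the test sentence means arm comparisons at 3 and at 12 months. It follows directly on the marker paragraph. It drops baseline, which fits SAP 5.3, where significance tests between arms on baseline variables are ruled out. The fallback wording is nearly that of SAP 6.2, where two arms are compared. The within-recipient comparison is only to be explored, with no test named in that sentence. On this reading Mann-Whitney is correct for the markers, and that part stands.

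It does not settle the drug levels. A comparison confined to adalimumab recipients cannot be an arm comparison, the paragraph later refers to both classes of outcome, and on its face it tests 3 against 12 months. If it was meant for arms only, the visit comparison has no named method. Either way the section needs separating.

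Three stronger inferences are tempting, and the documents do not support them:

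- That the plan prescribes an unpaired t-test. It says only a t-test, which may be paired. The demonstrable mismatch is the fallback, reached only after log-transformation fails, so the SE ratios of 1.20 to 1.83 do not describe a test the plan specifies.
- That the relation between drug level and primary outcome would go unexamined. The optional regressions in 6.4 carry no significance condition.
- That antibody levels are certainly affected. Section 6.4 gives no antibody-specific comparison, so the point reaches them only if they are compared over time.

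**Conclusion.** The point holds as a minor defect of specification. One test paragraph covers a paired and an unpaired comparison, and its non-parametric fallback is wrong for the paired one. If Mann-Whitney is used on the paired levels, and ρ lies between 0.3 and 0.7, its type I error is about 0.02 to below 0.001 instead of 0.05. Power for a 0.4 SD shift is about 0.54, where signed-rank would give 0.68 to 0.96. This rests on an assumed ρ, 55 complete pairs, equal variances and simulated normal data. There is no loss at ρ = 0. False positives would be inflated only if ρ were negative, for which the documents give no ground.

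The practical consequence is limited to correlations with the primary outcome that might not be triggered. The outcome is tertiary and hypothesis-generating, and no primary or secondary conclusion depends on it.

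**What to change.** Split the test paragraph in SAP 6.4 in two:

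- **Within-participant visit comparisons** of adalimumab levels, and of antibody levels if they are compared over time: paired t-test with Wilcoxon signed-rank as fallback, or a mixed model with a participant random effect.
- **Between-arm comparisons** of exploratory markers at 3 and at 12 months: two-sample t-test with Mann-Whitney as fallback.

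The cost is SAP wording only, with no new data, visits or participants. One small downside is that the simple paired tests drop anyone with only one of the two samples; the mixed model keeps them.
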